6.6.2. Urine Samples

Urine samples will be collected for the following laboratory analyses at every study visit, unless otherwise specified:

- Urinalysis and urine Chemistry: including color & clarity, specific gravity, pH, glucose, ketones, bilirubin, urobilinogen, blood, nitrite, leukocyte esterase and microscopic (if microscopic elements are seen), urine protein, albumin, creatinine, phosphate, calcium, magnesium and uric acid (**All visits except Days 2, 4, 8 and 9**)
- Urine pregnancy test (females of childbearing potential only). If the test is positive, confirmatory serum test should be sent and study drug dosing should be delayed until results obtained (**Day 1**)
- Urine storage (**All visits except Screening, Days 2, 4, 8 and 9**)

CCI

CCI

6.7. Management of Virologic Failure after Initiation of B/F/TAF on Day 10

Subjects who experience either suboptimal virologic response (SVR) or virologic rebound (VR) after initiating B/F/TAF, as defined below, will be considered to have virologic failure.

6.7.1. Suboptimal Virologic Response (SVR)

- HIV-1 RNA ≥ 50 copies/mL **and** less than 1 log₁₀ HIV-1 RNA reduction from Day 10 at the Day 57 visit

Following the first instance of SVR at Day 57, subjects will be asked to return to the clinic for a scheduled or unscheduled blood draw (2 to 3 weeks after first SVR visit) for confirmation of SVR. A plasma sample from either the first instance or the SVR confirmation visit will be tested for HIV-1 capsid genotypic and phenotypic resistance. In addition, if SVR is confirmed, a plasma sample from the SVR confirmation visit will be tested for HIV-1 PR, RT, and IN genotypic and phenotypic resistance.

6.7.2. Virologic Rebound (VR)

- At any visit, after achieving HIV-1 RNA < 50 copies/mL, a rebound in HIV-1 RNA to ≥ 50 copies/mL, which is subsequently confirmed at the following scheduled or unscheduled visit; OR
- At any visit, a $> 1 \log_{10}$ increase in HIV-1 RNA from the nadir which is subsequently confirmed at the following scheduled or unscheduled visit.

At any visit after achieving HIV-1 RNA < 50 copies/mL, if the HIV-1 RNA is ≥ 50 and < 200 copies/mL, a reflex HIV-1 RNA repeat test will be conducted on stored plasma samples, if available. If the repeat result is < 50 copies/mL, no further action is required. If the repeat result is ≥ 50 copies/mL subjects will be asked to return to the clinic for a scheduled or unscheduled blood draw (2 to 3 weeks after the date of the original test that resulted in HIV-1 RNA VR) for confirmation of VR.

A plasma sample from either the first instance or the VR confirmation visit will be tested for HIV-1 capsid genotypic and phenotypic resistance. In addition, if VR is confirmed, a plasma sample from the VR confirmation visit will be tested for HIV-1 PR, RT, and IN genotypic and phenotypic resistance.

7. ADVERSE EVENTS AND TOXICITY MANAGEMENT

7.1. Definitions of Adverse Events, Adverse Reactions, and Serious Adverse Events

7.1.1. Adverse Events

An adverse event (AE) is any untoward medical occurrence in a clinical study subject administered a medicinal product, which does not necessarily have a causal relationship with the treatment. An AE can therefore be any unfavorable and/or unintended sign, symptom, or disease temporally associated with the use of a medicinal product, whether or not considered related to the medicinal product. AEs may also include pre- or post-treatment complications that occur as a result of protocol specified procedures, lack of efficacy, overdose, drug abuse/misuse reports, or occupational exposure. Preexisting events that increase in severity or change in nature during or as a consequence of participation in the clinical study will also be considered AEs.

An AE does not include the following:

- Medical or surgical procedures such as surgery, endoscopy, tooth extraction, and transfusion. The condition that led to the procedure may be an adverse event and must be reported.
- Pre-existing diseases, conditions, or laboratory abnormalities present or detected before the screening visit that do not worsen
- Situations where an untoward medical occurrence has not occurred (e.g., hospitalization for elective surgery, social and/or convenience admissions)
- Overdose without clinical sequelae (see Section 7.7)
- Any medical condition or clinically significant laboratory abnormality with an onset date before the consent form is signed and not related to a protocol-associated procedure is not an AE. It is considered to be pre-existing and should be documented on the medical history eCRF.

7.1.2. Serious Adverse Events

A **serious adverse event** (SAE) is defined as an event that, at any dose, results in the following:

- Death
- Life-threatening (Note: The term “life-threatening” in the definition of “serious” refers to an event in which the subject was at risk of death at the time of the event; it does not refer to an event that hypothetically might have caused death if it were more severe.)
- In-patient hospitalization or prolongation of existing hospitalization

- Persistent or significant disability/incapacity
- A congenital anomaly/birth defect
- A medically important event or reaction: such events may not be immediately life-threatening or result in death or hospitalization but may jeopardize the subject or may require intervention to prevent one of the other outcomes constituting SAEs. Medical and scientific judgment must be exercised to determine whether such an event is a reportable under expedited reporting rules. Examples of medically important events include intensive treatment in an emergency room or at home for allergic bronchospasm; blood dyscrasias or convulsions that do not result in hospitalization; and development of drug dependency or drug abuse. For the avoidance of doubt, infections resulting from contaminated medicinal product will be considered a medically important event and subject to expedited reporting requirements.

7.2. Assessment of Adverse Events and Serious Adverse Events

The investigator or qualified subinvestigator is responsible for assessing AEs and SAEs for causality and severity, and for final review and confirmation of accuracy of event information and assessments.

7.2.1. Assessment of Causality for Study Drugs and Procedures

The investigator or qualified subinvestigator is responsible for assessing the relationship to IMP therapy using clinical judgment and the following considerations:

- **No:** Evidence exists that the adverse event has an etiology other than the IMP. For SAEs, an alternative causality must be provided (eg, pre-existing condition, underlying disease, intercurrent illness, or concomitant medication).
- **Yes:** There is reasonable possibility that the event may have been caused by the investigational medicinal product.

It should be emphasized that ineffective treatment should not be considered as causally related in the context of adverse event reporting.

The relationship to study procedures (eg, invasive procedures such as venipuncture or biopsy) should be assessed using the following considerations:

- **No: Evidence** exists that the adverse event has an etiology other than the study procedure.
- **Yes:** The adverse event occurred as a result of protocol procedures (eg., venipuncture).

7.2.2. Assessment of Severity

AE severity should be recorded and graded according to the Gilead Grading Scale for Severity of Adverse Events and Laboratory Abnormalities ([Appendix 4](#)).

The distinction between the seriousness and the severity of an adverse event should be noted.

Severe is a measure of intensity; thus, a severe reaction is not necessarily a serious reaction. For example, a headache may be severe in intensity, but would not be classified as serious unless it met one of the criteria for serious events.

7.3. Investigator Requirements and Instructions for Reporting Adverse Events and Serious Adverse Events to Gilead

Requirements for collection prior to study drug initiation:

After informed consent, but prior to administration of study drug, the following types of events should be reported on the case report form (eCRF): all SAEs and adverse events related to protocol-mandated procedures.

Adverse Events

Following administration of study drug, all AEs, regardless of cause or relationship, that occur on or before the last posttreatment follow-up visit, or in the case of early termination, 225 days after the administration of study drug must be reported to the eCRF database as instructed.

All AEs should be followed up until resolution or until the adverse event is stable, if possible. Gilead Sciences may request that certain AEs be followed beyond the protocol defined follow up period.

Serious Adverse Events

All SAEs, regardless of cause or relationship, that occurs after the subject first consents to participate in the study (ie, signing the informed consent) and throughout the duration of the study, including the protocol-required post treatment follow-up period, must be reported to the eCRF database and Gilead Pharmacovigilance and Epidemiology (PVE) as instructed. This also includes any SAEs resulting from protocol-associated procedures performed after informed consent is signed.

Any SAEs and deaths that occur on or before the last post-treatment follow-up visit, or in the case of early termination, 225 days after the administration of study drug, regardless of causality, should also be reported.

Severity should be recorded and graded according to the GSI Grading Scale for Severity of Adverse Events and Laboratory Abnormalities ([Appendix 4](#)). For AEs associated with laboratory abnormalities, the event should be graded on the basis of the clinical severity in the context of the underlying conditions; this may or may not be in agreement with the grading of the laboratory abnormality.

7.6. Toxicity Management

All clinical and clinically significant laboratory toxicities will be managed according to uniform guidelines detailed in [Appendix 3](#), and as outlined below. CCI

- Clinical events and clinically significant laboratory abnormalities will be graded according to the Gilead Grading Scale for Severity of Adverse Events and Laboratory Abnormalities ([Appendix 4](#)).
- Treatment-emergent toxicities will be noted by the investigator and brought to the attention of the Gilead medical monitor. Whether or not considered treatment-related, all subjects experiencing AEs must be monitored periodically as clinically indicated, until symptoms subside, and until any abnormal laboratory values have resolved or returned to baseline levels or they are considered irreversible, or until there is a satisfactory explanation for the changes observed.
- Grade 3 and 4 clinically significant laboratory abnormalities should be confirmed by repeat testing within 3 calendar days of receipt of results, unless such a delay is not consistent with good medical practice.

Any questions regarding toxicity management should be directed to the Gilead medical monitor.

7.7. Special Situations Reports

7.7.1. Definitions of Special Situations

Special situation reports include all reports of medication error, abuse, misuse, overdose, reports of adverse events associated with product complaints, and pregnancy reports regardless of an associated AE.

Medication error is any unintentional error in the prescribing, dispensing, or administration of a medicinal product while in the control of the health care provider, subject, or consumer.

Abuse is defined as persistent or sporadic intentional excessive use of a medicinal product by a subject.

Misuse is defined as any intentional and inappropriate use of a medicinal product that is not in accordance with the protocol instructions or the local prescribing information.

An overdose is defined as an accidental or intentional administration of a quantity of a medicinal product given per administration or cumulatively which is above the maximum recommended dose as per protocol or in the product labelling (as it applies to the daily dose of the subject in question). In cases of a discrepancy in drug accountability, overdose will be established only when it is clear that the subject has taken the excess dose(s). Overdose cannot be established when the subject cannot account for the discrepancy except in cases in which the investigator has reason to suspect that the subject has taken the additional dose(s).

Product complaint is defined as complaints arising from potential deviations in the manufacture, packaging, or distribution of the medicinal product.

Occupational exposure with an AE is defined as exposure to a medicinal product as a result of one's professional or non-professional occupation.

7.7.2. Instructions for Reporting Special Situations

7.7.2.1. Instructions for Reporting Pregnancies

The investigator should report pregnancies in female study subjects that are identified after administration of study drug and throughout the study, including the post study drug follow-up period, to the Gilead PVE using the pregnancy report form within 24 hours of becoming aware of the pregnancy.

Refer to Section 7.3 and the eCRF completion guidelines for full instructions on the mechanism of pregnancy reporting.

The pregnancy itself is not considered an AE nor is an induced elective abortion to terminate a pregnancy without medical reasons.

Any premature termination of pregnancy (eg, a spontaneous abortion, an induced therapeutic abortion due to complications or other medical reasons) must be reported within 24 hours as an SAE. The underlying medical reason for this procedure should be recorded as the AE term.

A spontaneous abortion is always considered to be an SAE and will be reported as described in Section 7.1.2. Furthermore, any SAE occurring as an adverse pregnancy outcome post study must be reported to Gilead PVE.

The subject should receive appropriate monitoring and care until the conclusion of the pregnancy. The outcome should be reported to or Gilead PVE using the pregnancy outcome report form. If the end of the pregnancy occurs after the study has been completed, the outcome should be reported directly to Gilead PVE. Gilead PVE contact information is as follows:

Email: PPD and Fax: PPD

Pregnancies of female partners of male study subjects exposed to Gilead or other study drugs must also be reported and relevant information should be submitted to Gilead PVE using the pregnancy and pregnancy outcome forms within 24 hours. Monitoring of the subject should continue until the conclusion of the pregnancy. If the end of the pregnancy occurs after the study has been completed, the outcome should be reported directly to Gilead PVE, fax number PPD or email PPD

Refer to [Appendix 6](#) for Pregnancy Precautions, Definition for Female of Childbearing Potential, and Contraceptive Requirements.

7.7.2.2. Reporting Other Special Situations

All other special situation reports must be reported on the special situations report form and forwarded to Gilead PVE within 24 hours of the investigator becoming aware of the situation. These reports must consist of situations that involve study IMP and/or Gilead concomitant medications, but do not apply to non-Gilead concomitant medications.

Special situations involving non-Gilead concomitant medications do not need to be reported on the special situations report form; however, for special situations that result in AEs due to a non-Gilead concomitant medication, the AE should be reported on the AE form.

Any inappropriate use of concomitant medications prohibited by this protocol should not be reported as “misuse,” but may be more appropriately documented as a protocol deviation.

Refer to Section [7.3](#) and the eCRF completion guidelines for full instructions on the mechanism of special situations reporting.

All clinical sequelae in relation to these special situation reports will be reported as AEs or SAEs at the same time using the AE eCRF and/or the SAE report form. Details of the symptoms and signs, clinical management, and outcome will be reported, when available.

8. STATISTICAL CONSIDERATIONS

8.1. Analysis Objectives and Endpoints

8.1.1. Analysis Objectives

Part A (Cohorts 1 – 5):

The primary analysis objective of this study is to evaluate the short-term antiviral activity of GS-6207 compared to placebo administered subcutaneously (SC) in the abdomen on Day 1, with respect to the maximum reduction of plasma HIV-1 RNA (\log_{10} copies/mL) from Day 1 through Day 10 in HIV-1 infected adult subjects who are antiretroviral treatment naïve or are experienced but capsid inhibitor (CAI) naïve.

The secondary analysis objectives of this study are to investigate the safety and tolerability of GS-6207 as compared to placebo, to characterize the plasma pharmacokinetic (PK) of GS-6207 and the PK/pharmacodynamic (PD) (or dose-response) relationship between GS-6207 concentration at Day 10 and the viral dynamics of HIV-1, to determine the number and percentage of subjects ever achieving HIV-1 RNA < 50 copies/mL by Day 10, and to examine any emergence of CAI resistance.

Part B (Cohorts 6 - 8):

The primary analysis objective of this study is to evaluate the short-term antiviral activity of a single dose of oral TAF with respect to the maximum reduction of plasma HIV-1 RNA (\log_{10} copies/mL) from Day 1 through Day 10 in HIV-1 infected adult subjects who are antiretroviral treatment naïve or are experienced but without resistance to TAF.

The secondary analysis objectives of this study are to investigate the safety and tolerability of TAF, to characterize the PK of TAF, and to examine any emergence of TAF resistance.

CCI

8.1.2. Primary Endpoint

The primary endpoint is the maximum reduction of plasma HIV-1 RNA (\log_{10} copies/mL) from Day 1 through Day 10.

8.1.3. Secondary Endpoint

Secondary endpoints include:

- Incidences of adverse events and graded laboratory abnormalities
- PK parameters of GS-6207 (Part A) and TAF (and its metabolites, as appropriate) (Part B)
- Correlation between C_t (concentration at Day 10) of GS-6207 (Part A) and the maximum reduction of plasma HIV-1 RNA (\log_{10} copies/mL) from baseline through Day 10
- Number and percentage of subjects ever achieving HIV-1 RNA < 50 copies/mL by Day 10 (Part A)
- Incidences of any emergence of CAI resistance (Part A)
- Incidences of any emergence of TAF resistance (Part B)

8.1.4. Other Endpoints of Interest

The correlation between AUC of TAF, and its metabolites, as appropriate, and the maximum reduction of plasma HIV-1 RNA (\log_{10} copies/mL) from baseline through Day 10.

8.2. Analysis Conventions

8.2.1. Analysis Sets

Analysis sets define which subjects are included in an analysis. The assignment of subjects to analysis sets will be done before the study blind is broken for analysis.

8.2.1.1. Efficacy

The primary analysis set for efficacy analysis is defined as full analysis set (FAS), which includes all subjects who are randomized and receive full dose of randomized study drug. Subjects with major eligibility violations that are identifiable based on pre-randomization characteristics may be excluded. Subjects will be grouped according to the treatment to which they are randomized.

8.2.1.2. Safety

The primary analysis set for safety analyses is defined as safety analysis set, which includes all subjects who are randomized and receive any dose of study drug. Subjects who receive treatment other than that intended will be analyzed according to treatment received.

8.2.1.3. Pharmacokinetics

The primary analysis set for PK analyses is defined as GS-6207 or TAF PK analysis set, which includes all subjects who are randomized, receive any dose of GS-6207 or TAF, and have at least 1 nonmissing post baseline concentration value for GS-6207 or TAF, or its metabolites.

8.2.1.4. Pharmacokinetic/Pharmacodynamic Analysis Set

The PK/PD analysis set includes all subjects who are in full analysis set and have both nonmissing C_t of GS-6207 and the maximum reduction of plasma HIV-1 RNA (\log_{10} copies/mL) from Day 1 through Day 10.

8.3. Data Handling Conventions

Logarithm (base 10) transformation will be applied to HIV-1 RNA levels for efficacy analysis. Natural logarithm transformation for all PK parameters of GS-6207, TAF, and its metabolites (eg, C_{max} , C_t , and AUC_{0-t} , as applicable) will be applied for pharmacokinetic analysis.

For summary statistics, PK concentration values below the limit of quantitation (BLQ) will be treated as zero at pre-dose and one-half of the lower limit of quantitation (LLOQ) for post dose time points.

Laboratory data that are continuous in nature but are less than the LLOQ or above the upper limit of quantitation will be imputed to the value of the lower or upper limit minus or plus 1 significant digit, respectively (eg, if the result of a continuous laboratory test is < 20 , a value of 19 will be assigned; if the result of a continuous laboratory test is < 20.0 , a value of 19.9 will be assigned).

8.4. Demographic Data and Baseline Characteristics

Demographic and baseline characteristics will be summarized and descriptive statistics will be provided.

Demographic summaries will include sex, race, ethnicity, and age.

Baseline data will include a summary of body weight, height, and body mass index.

8.5. Efficacy Analysis

8.5.1. Primary Analysis

Data from the placebo recipients in all cohorts will be combined to form one placebo group for the purpose of analysis. Each of the GS-6207 and TAF treatment group will be compared to the pooled placebo group with respect to the primary efficacy endpoint, the maximum reduction of plasma HIV-1 RNA (\log_{10} copies/mL) from Day 1 through Day 10, using the 2-sided t-test conducted at an alpha level of 0.05.

8.5.2. Secondary Analyses

Correlation between C_t of GS-6207 and the maximum reduction of HIV-1 RNA (\log_{10} copies/mL) from Day 1 through Day 10 will be assessed using the Pearson correlation analysis. Analysis will be done for each treatment group.

The percentage of subjects ever achieving HIV-1 RNA < 50 copies/mL by Day 10 (for Part A only) will be summarized by treatment group. Fisher exact test will be used for comparison between treatment groups.

Percentage of subjects with any emergence of CAI resistance and TAF resistance, respectively, will be summarized by treatment group.

8.6. Safety Analysis

All safety data collected on or after the first dose date will be summarized by treatment according to the study drug received. Data for the pretreatment period will be included in data listings.

8.6.1. Duration of Exposure

A subject's extent of exposure to study drug data will be generated from the study drug administration eCRF form. Exposure data will be listed.

8.6.2. Adverse Events

Clinical and laboratory adverse events will be coded using the Medical Dictionary for Regulatory Activities (MedDRA). System Organ Class (SOC), High-Level Group Term (HLGT), High-Level Term (HLT), Preferred Term (PT), and Lower-Level Term (LLT) will be attached to the clinical database.

Events will be summarized on the basis of the date of onset for the event. A treatment-emergent adverse event will be defined as any adverse event that begins on or after the date of first dose of study drug.

Summaries (number and percentage of subjects) of treatment-emergent adverse events (by SOC, and PT) will be provided by treatment group. Additional summaries will include summaries for adverse events by grade, Investigator's assessment of relationship to study drug, and effect on study drug dosing.

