1.2.2.1. GS-US-200-4070 Summary

Study GS-US-200-4070 is an ongoing, Phase 1 study in healthy volunteers evaluating the safety, tolerability, and PK of single ascending doses of a GS-6207 subcutaneous suspension. 40 unique subjects across 4 dosing cohorts have received either SC GS-6207 or placebo (4:1 ratio). Administration of single SC doses of GS-6207 30 mg (Cohort 1), 100 mg (Cohort 2), 300 mg (Cohort 3) and 450 mg (Cohort 4) is complete. PK sampling for Cohorts 1 and 2 (through Day 169 [24 weeks] post dose) is complete and ongoing for Cohorts 3 and 4 (through Day 225 [32 weeks] post dose). Preliminary PK profiles and PK parameters of subcutaneous GS-6207 administered as single doses of 30 mg, 100 mg, 300 mg and 450 mg are presented in [Figure 1-1](#) and [Table 1-1](#) below. Preliminary PK data are available for 168 days post dose for Cohorts 1, 2 and 4, and through 196 days post-dose for Cohort 3.

GS-6207 PK profiles ([Table 1-1](#)) are consistent with sustained delivery. The PK is characterized by prolonged exposure, with measurable concentrations for up to 196 days [28 weeks], to date. The median apparent terminal $t_{1/2}$ is 30-43 days. Increases in GS-6207 mean C_{max} and AUC_{inf} are approximately dose proportional over the dose range of 30-450 mg.

In a preliminary blinded review of the available safety data through February 1, 2019 (n=40), no deaths, serious adverse events (SAEs), or Grade 3-4 adverse events (AEs) have been reported. Injection site reactions occurred in 21 of 40 subjects (53%) these included injection site erythema (15 subjects, 38%), injection site pain (14 subjects, 35%), injection site nodules (9 subjects, 23%), injection site induration (8 subjects, 20%), and injection site swelling (7 subjects, 18%). The only other AE that was reported by more than 10% of subjects was headache (5/40, 13%).

Figure 1-1. Preliminary Mean (SD) GS-6207 Plasma Concentration-Time Profiles Following Single-Dose Administration of Subcutaneous Suspension of GS-6207 30 mg, 100 mg, 300 mg and 450mg (N=8 per cohort)

[figure not shown]

Table 1-1. Study GS-US-200-4070 Preliminary Plasma Pharmacokinetic Parameters of GS-6207 Following Single Dose Administration of Subcutaneous Suspension of GS-6207, 30-450 mg

	Cohort 1 N=8	Cohort 2 N=8	Cohort 3 N=8	Cohort 4 N=8
Dose (Injection Volume)	30 mg (1 x 0.3 mL)	100 mg (1 x 1 mL)	300 mg (3 x 1 mL)	450 mg (3 x 1.5 mL)
PK Parameter Mean (%CV)				

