#### **7.1.2. Adverse Event Severity**

Adverse events are graded by the investigator as Grade 1, 2, 3, or 4 according to toxicity criteria specified in the protocol. The severity grade of events for which the investigator did not record severity will be categorized as “missing” for tabular summaries and data listings. The missing category will be listed last in summary presentation.

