##### **7.1.6.1. Summaries of AE Incidence in Combined Severity Grade Subsets**

A brief, high-level summary of the number and percentage of subjects who experienced at least 1 TEAE in the categories described below will be provided by treatment group for TEAEs with onset date reported up to Day 10 (prior to the B/F/TAF first dose date) and throughout the study, respectively. All deaths observed in the study will also be included in this summary.

The number and percentage of subjects who experienced at least 1 TEAE will be provided and summarized by SOC, HLT (if applicable), PT, and treatment group.

- TEAEs

For the AE categories described below, summaries will be provided by SOC, PT, and treatment group:

- TEAEs with Grade 3 or higher (by severity)
- TE treatment-related AEs
- TE treatment-related AEs with Grade 3 or higher (by severity)
- TEAEs leading to death (ie, outcome of death)
- TE SAEs
- TE treatment-related SAEs
- TEAEs leading to premature discontinuation of study drug
- TEAEs leading to premature discontinuation of study

Multiple events will be counted only once per subject in each summary. Adverse events will be summarized and listed first in alphabetic order of SOC (and HLT within each SOC if applicable), and then by PT in descending order of total frequency within each SOC. For summaries by severity grade, the most severe grade will be used for those AEs that occurred more than once in an individual subject during the study.

In addition to the above summary tables, for the AE categories described below, summaries will be provided by PT only in descending order of total frequency:

- TEAEs
- TE SAEs

In addition, data listings will be provided for the following:

- All AEs
- All SAEs
- All Deaths
- All AEs leading to death (ie, outcome of death)
- All AEs with severity of Grade 3 or higher
- All AEs leading to premature discontinuation of study drug
- All AEs leading to premature discontinuation of study
- All AEs for COVID-19 and Suspected COVID-19 infection, defined as AE preferred terms of “Suspected COVID-19”, “COVID-19”, “COVID-19 pneumonia”, or “Asymptomatic COVID-19”

For each listing, whether the event is treatment emergent will be indicated.

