**7.7. Changes from Protocol-Specified Safety Analyses**

There are no deviations from the protocol-specified safety analyses.

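### The protocol plans adverse event summaries by grade, but the SAP tabulates severity only at Grade 3 or higher and declares no deviation, so no planned table separates Grade 1 from Grade 2

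*Protocol*

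**What the plan says.** Protocol 8.6.2 plans TEAE tables by system organ class (SOC) and preferred term (PT), then adds: "Additional summaries will include summaries for adverse events by grade, Investigator's assessment of relationship to study drug, and effect on study drug dosing". The grades are not limited.

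SAP 7.1.6.1 lists the adverse event tables. Severity enters two of them: "TEAEs with Grade 3 or higher (by severity" and "TE treatment-related AEs with Grade 3 or higher (by severity". The overall TEAE table and the table of all treatment-related TEAEs carry no grade split.

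Two other SAP statements bear on severity:
- SAP 7.1.6.1 gives a counting rule: "For summaries by severity grade, the most severe grade will be used".
- SAP 7.1.2 recognises Grades 1 to 4 and puts ungraded events in a missing category for tables and listings: "The missing category will be listed last in summary presentation".

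On changes from the protocol, SAP 7.7 says: "There are no deviations from the protocol-specified safety analyses".

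**The concern.** Safety and tolerability against placebo is the first secondary objective of Part A. A protocol-specified summary that serves it is absent from the SAP's list, and the section meant to record such changes reports none. The SAP does declare changes elsewhere (6.4 for efficacy, 8.3.3 for pharmacokinetics), so a reader of the study report would take 7.7 at face value.

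The missing part is where the events are expected. For the 40 subjects in the earlier study of this suspension, Protocol 1.2.2.1 reports that "no deaths, serious adverse events (SAEs), or Grade 3-4 adverse events (AEs) have been reported", while about half had injection site reactions. Under the grading scale in Protocol Appendix 4, an adult local reaction reaches Grade 3 only with complications such as ulceration, secondary infection or sterile abscess. The step from Grade 1 to Grade 2 is one of size for local reactions, and of effect on limb use or daily activity for pain. SAP 1.2 plans from one to five injections per dose across cohorts, so a reader comparing doses would want that step tabulated.

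**Working it through.** The documents state no design figure on this point, so the check is a comparison of text followed by a forecast of how full the Grade 3+ tables would be.

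**1. Text.** Protocol 8.6.2 asks for summaries by grade with no threshold. Both severity tables in SAP 7.1.6.1 start at Grade 3. The other TEAE tables count subjects with any event regardless of grade. No listed table shows Grade 1 and Grade 2 separately. By contrast, SAP 7.2.2.2 tabulates laboratory abnormalities across all grades and adds a separate Grade 3 or 4 table.

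**2. What the tables could not distinguish (hypothetical).** Take a dose group of 6 with five subjects at worst Grade 1, and another with five at worst Grade 2. Both give 5/6 any grade and 0/6 Grade 3 or higher, so their planned tables are identical.

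**3. Injection site reactions, inputs.** 21 of 40 subjects (Protocol 1.2.2.1), of whom 32 were active and 8 placebo (Protocol 1.5.1). Active Part A participants: 5 cohorts × 6 = 30.
- Pooled rate: 21/40 = 52.5%, which agrees with the stated 53%. Applied to 30: 0.525 × 30 = 15.75, about 16.
- The pool is blinded, so the active rate is only bounded. If all 8 placebo subjects reacted, it is 13/32 = 40.6%, or about 12 of 30. If none did, it is 21/32 = 65.6%, or about 20 of 30.
- As none of the 40 had a Grade 3-4 event, all 21 fall below the SAP's cut.

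**4. Upper limit for the Grade 3+ rate after zero events.** Exact two-sided 95% limit: 1 − 0.025^(1/n).
- n = 40 (pooled): 1 − 0.025^(1/40) = 8.8%.
- n = 32 (active only): 1 − 0.025^(1/32) = 10.9%.

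**5. Chance that no active Part A participant appears in the Grade 3+ table.** (1 − p)^30, with p assumed:
- p = 1%: 0.99^30 = 0.74
- p = 3%: 0.97^30 = 0.40
- p = 5%: 0.95^30 = 0.21
- p = 8.8%: 0.912^30 = 0.06

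**6. Per dose group of 6.** At p = 8.8% the expected number with a Grade 3+ event is 6 × 0.088 = 0.53, and the chance of none is 0.912^6 = 0.58. At p = 5% these are 0.30 and 0.95^6 = 0.74.

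An entirely empty table is thus likely only at the low end of the range. Within a dose group, about half a subject or fewer is expected for rates up to 8.8%.

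**The case against.** The protocol wording is brief. It does not say maximum grade, or each grade separately, whereas Protocol 8.6.3 does specify maximum toxicity grade for laboratory data. Two Grade 3+ tables could be called summaries by grade, and SAP 7.7 would then be accurate. This reading is strained. A summary confined to the top of the scale leaves most of it unsummarised, and the missing category in SAP 7.1.2 has no natural place in a Grade 3+ table. That category and the worst-grade rule suggest that an all-grade table may have been intended and left off the list. If so, the remedy is the same.

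The information is not lost. Grades are collected and a listing of all adverse events is planned. With six participants per dose, a reader could count grades by hand. That stands, and it limits the harm to the summary tables, but a listing is not the summary that the protocol specifies.

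A reader might infer that the severity tables will be nearly empty. The documents do not support that as a fact. The prior data are blinded, mix active with placebo, and come mostly from healthy volunteers, and the safety review of Cohort 1 in this study was made when it had completed only Day 10. The SAP tables run to Day 225, on B/F/TAF from Day 10. Part B includes TAF 600 mg, while Protocol 1.5.2 calls safety above 125 mg unknown.

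A reader might also infer that dose choice for later phases depends on these tables. It need not. Protocol 8.9 and SAP 2.1 place dose selection in unblinded interim reviews under a charter, and SAP 1 describes outputs for the study report.

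Nor do the documents say that a dose effect would appear as a shift from Grade 1 to Grade 2. It could appear as any-grade incidence, which is tabulated.

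**Conclusion.** The discrepancy holds on the text alone. A summary specified in Protocol 8.6.2 is cut to Grade 3 or higher in SAP 7.1.6.1, and SAP 7.7 is wrong to report no deviation. The practical loss is the split between Grades 1 and 2 by dose, chiefly for injection site reactions.

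The Grade 3+ tables are likely to be sparse and to miss most tolerability events. This assumes that the earlier healthy-volunteer experience carries over to this population and this follow-up. How sparse depends on a rate that the documents do not give: the chance of no active Part A participant runs from 74% at 1% to 6% at 8.8%. The primary endpoint is unaffected, and the gap can be closed from data already planned for collection.

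**What to change.** In SAP 7.1.6.1, add two tables: all TEAEs and treatment-related TEAEs, each by maximum grade (1, 2, 3, 4, missing), by SOC, PT and treatment group. Produce both for events up to Day 10 and throughout the study, the two periods that the SAP already uses for its high-level summary. SAP 7.7 can then stand on this point. If the tables are not added, state in SAP 7.7 that severity summaries are restricted to Grade 3 or higher.

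The cost is two table layouts. Since the SAP reports Parts A and B separately, that makes 2 × 2 periods × 2 parts = 8 outputs, all from existing adverse event data. The alternative costs one sentence in 7.7.
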